7.2.2 Reporting of Pregnancy and Lactation to the Sponsor and to Merck

Although pregnancy and infant exposure during breast feeding are not considered adverse events, it is the responsibility of investigators or their designees to report any pregnancy or lactation in a participant (spontaneously reported to them) that occurs during the study.

Pregnancies and infant exposures during breastfeeding that occur after the consent form is signed but before treatment allocation/randomization must be reported by the investigator if they cause the participant to be excluded from the trial, or are the result of a protocol-specified intervention, including but not limited to washout or discontinuation of usual therapy, diet, placebo treatment or a procedure.

Pregnancies and infant exposures during breastfeeding that occur from the time of treatment allocation/randomization through 120 days following cessation of Sponsor's product, or 30 days following cessation of treatment if the participant initiates new anticancer therapy, whichever is earlier, must be reported by the investigator. All reported pregnancies must be followed to the completion/termination of the pregnancy. Pregnancy outcomes of spontaneous abortion, missed abortion, benign hydatidiform mole, blighted ovum, fetal death, intrauterine death, miscarriage and stillbirth must be reported as serious events (Important Medical Events). If the pregnancy continues to term, the outcome (health of infant) must also be reported.

Such events must be reported within 24 hours to the Sponsor and within 2 working days to Merck Global Safety. (Attn: Worldwide Product Safety; [contact])

Immediate Reporting of Adverse Events to the Sponsor and to Merck

7.2.3.1 Serious Adverse Events

A serious adverse event is any adverse event occurring at any dose or during any use of Merck's product that:

- Results in death;
- Is life threatening;
- Results in persistent or significant disability/incapacity;
- Results in or prolongs an existing inpatient hospitalization;
- Is a congenital anomaly/birth defect;
- Is another important medical event
- Note: In addition to the above criteria, adverse events meeting either of the below criteria, although not serious per ICH definition, are reportable to the Merck in the same timeframe as SAEs to meet certain local requirements. Therefore, these events are considered serious by Merck for collection purposes.
- Is a new cancer (that is not a condition of the study);
- Is associated with an overdose.

HCC 18-087

Refer to Table 7 for additional details regarding each of the above criteria.

For the time period beginning when the consent form is signed until start of treatment, any serious adverse event, or follow up to a serious adverse event, including death due to any cause that occurs to any participant must be reported within 24 hours to the Sponsor and within 2 working days to Merck Global Safety if it causes the participant to be excluded from the trial, or is the result of a protocol-specified intervention, including but not limited to washout or discontinuation of usual therapy, diet, placebo treatment or a procedure.

For the time period beginning at treatment allocation/randomization through 90 days following cessation of treatment, or 30 days following cessation of treatment if the participant initiates new anticancer therapy, whichever is earlier, any serious adverse event, or follow up to a serious adverse event, including death due to any cause whether or not related to the Merck product, must be reported within 24 hours to the Sponsor and within 2 working days to Merck Global Safety.

Additionally, any serious adverse event, considered by an investigator who is a qualified physician to be related to Merck product that is brought to the attention of the investigator at any time following consent through the end of the specified safety follow-up period specified in the paragraph above, or at any time outside of the time period specified in the previous paragraph also must be reported immediately to Merck Global Safety.

All participants with serious adverse events must be followed up for outcome.

SAE reports and any other relevant safety information are to be forwarded to the Merck Global Safety [contact]

A copy of all 15 Day Reports and Annual Progress Reports is submitted as required by FDA, European Union (EU), Pharmaceutical and Medical Devices agency (PMDA) or other local regulators. Investigators will cross reference this submission according to local regulations to the Merck Investigational Compound Number (IND, CSA, etc.) at the time of submission. Additionally investigators will submit a copy of these reports to Merck & Co., Inc. (Attn: Worldwide Product Safety; [contact]) at the time of submission to FDA.

7.2.3.2 Events of Clinical Interest

Version Dated 5-20-2021

Selected non-serious and serious adverse events are also known as Events of Clinical Interest (ECI) and must be reported within 2 working days to Merck Global Safety. (Attn: Worldwide Product Safety; [contact]).

For the time period beginning when the consent form is signed until treatment allocation/randomization, any ECI, or follow up to an ECI, that occurs to any participant must be reported within 2 working days to Merck Global Safety if it causes the participant to be excluded from the trial, or is the result of a protocol-specified intervention, including but not limited to washout or discontinuation of usual therapy, diet, placebo treatment or a procedure.

For the time period beginning at treatment allocation/randomization through 90 days following cessation of treatment, or 30 days following cessation of treatment if the participant initiates

new anticancer therapy, whichever is earlier, any ECI, or follow up to an ECI, whether or not related to Merck product, must be reported within 2 working days to Merck Global Safety.

Events of clinical interest for this trial include:

- 1. an overdose of Merck product, as defined in Section 7.2.1 Definition of an Overdose for This Protocol and Reporting of Overdose to the Sponsor, that is not associated with clinical symptoms or abnormal laboratory results.
- 2. an elevated AST or ALT lab value that is greater than or equal to 3X the upper limit of normal and an elevated total bilirubin lab value that is greater than or equal to 2X the upper limit of normal and, at the same time, an alkaline phosphatase lab value that is less than 2X the upper limit of normal, as determined by way of protocol-specified laboratory testing or unscheduled laboratory testing.*

*Note: These criteria are based upon available regulatory guidance documents. The purpose of the criteria is to specify a threshold of abnormal hepatic tests that may require an additional evaluation for an underlying etiology.

7.2.4 Evaluating Adverse Events

An investigator who is a qualified physician will evaluate all adverse events according to the NCI Common Terminology for Adverse Events (CTCAE), version 5.0. Any adverse event which changes CTCAE grade over the course of a given episode will have each change of grade recorded on the adverse event case report forms/worksheets.

All adverse events regardless of CTCAE grade must also be evaluated for seriousness.

Table 7 Evaluating Adverse Events

An investigator who is a qualified physician, will evaluate all adverse events as to:

Grade 1	Mild; asymptomatic or mid symptoms; clinical or diagnostic observations only; intervention not indicated.						
Grade 2	Moderate; minimal, local or noninvasive intervention indicated; limiting age-appropriate instrumental ADL.						
Grade 3	Severe or medically significant but not immediately life-threatening; hospitalization or prolongation or hospitalization indicated; disabling; limiting self-care ADL.						
Grade 4	Life threatening consequences; urgent intervention indicated.						
Grade 5	Death related to AE						
A serious adv	verse event is any adverse event occurring at any dose or during any use of Merck product that:						
†Results in d	leath; or						
	Itening; or places the participant, in the view of the investigator, at immediate risk of death from the event as it occurred (Note: This does not include an that, had it occurred in a more severe form, might have caused death.); or						
†Results in a	a persistent or significant disability/incapacity (substantial disruption of one's ability to conduct normal life functions); or						
hospitalizatio worsened is n	or prolongs an existing inpatient hospitalization (hospitalization is defined as an inpatient admission, regardless of length of stay, even if the in is a precautionary measure for continued observation. (Note: Hospitalization for an elective procedure to treat a pre-existing condition that has not not a serious adverse event. A pre-existing condition is a clinical condition that is diagnosed prior to the use of a Merck product and is documented in the dical history.); or						
†Is a congen	ital anomaly/birth defect (in offspring of participant taking the product regardless of time to diagnosis);or						
Is a new cancer (that is not a condition of the study) (although not serious per ICH definition, is reportable to the Sponsor within 24 hours and to working days to meet certain local requirements); or							
overdose that	se (whether accidental or intentional). Any adverse event associated with an overdose is considered a serious adverse event for collection purposes. An tis not associated with an adverse event is considered a non-serious event of clinical interest and must be reported within 24 hours to the Sponsor and to a 2 working days						
	Grade 3 Grade 4 Grade 5 A serious adverse even the sults in a t						

	based upon appr	Other important medical events that may not result in death, not be life threatening, or not require hospitalization may be considered a serious adverse event when, based upon appropriate medical judgment, the event may jeopardize the participant and may require medical or surgical intervention to prevent one of the outcomes listed previously (designated above by a †).							
Duration	Record the start	and stop dates of the adverse event. If less than 1 day, indicate the appropriate length of time and units							
Action taken	Did the adverse	event cause Merck product to be discontinued?							
Relationship to Merck Product	is a qualified ph medically qualif as reference gui information. The following c	uct cause the adverse event? The determination of the likelihood that Merck product caused the adverse event will be provided by an investigator who ysician. The investigator's signed/dated initials on the source document or worksheet that supports the causality noted on the AE form, ensures that a fied assessment of causality was done. This initialed document must be retained for the required regulatory time frame. The criteria below are intended delines to assist the investigator in assessing the likelihood of a relationship between the test drug and the adverse event based upon the available components are to be used to assess the relationship between Merck product and the AE; the greater the correlation with the components and their ents (in number and/or intensity), the more likely Merck product caused the adverse event (AE):							
	Exposure	Is there evidence that the participant was actually exposed to Merck product such as: reliable history, acceptable compliance assessment (pill count, diary, etc.), expected pharmacologic effect, or measurement of drug/metabolite in bodily specimen?							
	Time Course	Did the AE follow in a reasonable temporal sequence from administration of Merck product? Is the time of onset of the AE compatible with a drug-induced effect (applies to trials with investigational medicinal product)?							
	Likely Cause	Is the AE not reasonably explained by another etiology such as underlying disease, other drug(s)/vaccine(s), or other host or environmental factors							

Relationship	The following	components are to be used to assess the relationship between the test drug and the AE: (continued)
to Merck Product	Dechallenge	Was Merck product discontinued or dose/exposure/frequency reduced?
(continued)		If yes, did the AE resolve or improve?
(continued)		If yes, this is a positive dechallenge. If no, this is a negative dechallenge.
		(Note: This criterion is not applicable if: (1) the AE resulted in death or permanent disability; (2) the AE resolved/improved despite continuation of the Sponsor's product; or (3) the trial is a single-dose drug trial); or (4) Sponsor's product(s) is/are only used one time.)
	Rechallenge	Was the participant re-exposed to Merck product in this study?
		If yes, did the AE recur or worsen?
		If yes, this is a positive rechallenge. If no, this is a negative rechallenge.
		(Note: This criterion is not applicable if: (1) the initial AE resulted in death or permanent disability, or (2) the trial is a single-dose drug trial); or (3) Sponsor's product(s) is/are used only one time).
		NOTE: IF A RECHALLENGE IS PLANNED FOR AN ADVERSE EVENT WHICH WAS SERIOUS AND WHICH MAY HAVE BEEN CAUSED BY MERCK PRODUCT, OR IF REEXPOSURE TO MERCK PRODUCT POSES ADDITIONAL POTENTIAL SIGNIFICANT RISK TO THE PARTICIPANT, THEN THE RECHALLENGE MUST BE APPROVED IN ADVANCE BY THE SPONSOR AS PER DOSE MODIFICATION GUIDELINES IN THE PROTOCOL.
	Consistency with Trial Treatment Profile	Is the clinical/pathological presentation of the AE consistent with previous knowledge regarding Merck product or drug class pharmacology or toxicology?
	f relationship will the above elements	be reported on the case report forms /worksheets by an investigator who is a qualified physician according to his/her best clinical judgment, including is.
Record one of th	e following	Use the following scale of criteria as guidance (not all criteria must be present to be indicative of Merck product relationship).
Yes, there is a re possibility of Me relationship.		There is evidence of exposure to Merck product. The temporal sequence of the AE onset relative to the administration of Merck product is reasonable. The AE is more likely explained by Merck product than by another cause.
No, there is not a reasonable possibility of Merck product relationship		Participant did not receive the Merck product OR temporal sequence of the AE onset relative to administration of Merck product is not reasonable OR the AE is more likely explained by another cause than the Merck product. (Also entered for a participant with overdose without an associated AE.)

7.2.5 Sponsor Responsibility for Reporting Adverse Events

All Adverse Events will be reported to regulatory authorities, IRB/IECs and investigators in accordance with all applicable global laws and regulations.

8.0 STATISTICAL ANALYSIS PLAN

8.1 Statistical Analysis Plan Summary

Objectives

This trial will evaluate the anti-tumor efficacy of pembrolizumab in conjunction with IP cisplatin/rintatolimod. In addition to immunologic efficacy, a second objective is further monitoring of patient safety and adverse events. Provision is made to suspend the trial if unexpected and serious toxicities occur or if dose limiting toxicities (DLTs) from the list below in excess of 30% are observed:

- a) Any death not clearly due to the underlying disease or extraneous causes
- b) Any AE leading to a dose delay of greater than 14 days in initiation of cycle 2 will be considered a DLT
- c) A DLT is specifically defined as any of the following toxicities that occur related to any of the study interventions (cisplatin, rintatolimod, pembrolizumab) or the combination (as assessed by the Investigator) that occurs during the first cycle of treatment:
 - 1. Grade 3 renal toxicity
 - 2. Grade 2 or greater bronchospasm
 - 3. Grade 2 or greater allergic reaction or generalized urticaria
 - 4. Grade 2 or greater autoimmune reaction
 - 5. Grade 3 injection site reactions
 - 6. Grade 3 anaphylaxis
 - 7. Grade 2 pneumonitis
 - 8. ≥ Grade 3 hematologic toxicities lasting more than 48 hours, including neutropenia, thrombocytopenia and hemorrhage
 - 9. ≥ Grade 3 non-hematologic toxicities
 - 10. Grade 3 neurological symptoms
 - 11. Fever > 41°C, uncontrolled for over 4 hours in the absence of a medical cause
 - 12. Grade 3 diarrhea, Grade 3 skin toxicity, or Grade 3 liver function test increase
 - 13. Evaluation of liver toxicity as defined by Hy's Law:
 - The drug causes hepatocellular injury, generally shown by a higher incidence of 3-fold or greater elevations above the ULN of ALT or AST
 - Total Bilirubin>2xULN, without initial findings of cholestasis (elevated serum alkaline phosphatase)

Efficacy Study Design and Endpoints

The primary clinical endpoint is objective response. A secondary, translational endpoint is increase in the CD8 TIL infiltration in tumor and/or IP washes (pre-treatment vs post-treatment),

The primary endpoint is the objective response rate (rate of CR+PR by RECIST 1.1) at 13 weeks. Based on Ten Tije and Wils et al, the intent-to-treat objective response rate for IP cisplatin alone in platinum-sensitive recurrent ovarian cancer was approximately 45% 51 . An increase from 45% to 65% among response-evaluable patients would be of sufficient interest to warrant further study of the addition of rintatolimod and pembrolizumab in the presence of an acceptable safety profile. An optimal Simon two stage design with $\alpha = \beta = .10$ has been selected that will require 20 patients in the first stage and 25 in the second. In the first stage, 12 patients must have a response (PR or CR) in order to continue to the second stage. If the trial continues to the second stage and accrues 25 more patients and there are 25 or more patients with an objective response among the total of 45 treated, the study will be considered successful at demonstrating increase efficacy compared to cisplatin alone. The probability of early termination if the response rate is 45% is .59.

Continuous Monitoring of RLTs during the Study

Subject safety will be monitored continuously using Bayesian methods. If the posterior probability is .80 or greater that 30% or more of treated subjects experience a treatment related RLT as defined above, the RLT rate would be unacceptable and the study will be suspended pending review by the DSMC. This posterior probability will be calculated from the study's accumulating data and a weakly informative prior distribution. If π denotes a random variable representing the proportion of subjects who will experience a treatment related RLT, we assume π has a beta distribution with parameters a = 1.2 and b = 2.8 which assumes a mean of 30%. The table below describes the number of RLTs per number of treated patients that would trigger suspension. The table also shows the posterior probability that the RLT rate exceeds 33% and the binomial probability associated with the decision for an assumed 33% RLT rate.

Table 8: Number of RLTs per Number of Patients Treated Needed to Trigger Suspension

Subjects	Treatment-Related RLTs	$PP(\pi > 30\%)*$	$Pr(X \ge r p = .30)$
6	4	.903	.070
9	5	.904	.099
12	6	.890	.118
15	7	.880	.131
17	8	.903	.105
20	9	.896	.113
23	10	.891	.197
26	11	.886	.125
29	12	.883	.129
32	13	.880	.133

35	14	.877	.135
38	15	.876	.137
41	16	.874	.138
44	17	.873	.139

* π is the RLT rate. The minimum acceptable upper bound of a treatment-related RLT is 30%. PP(π > 30%) is the posterior probability that the RLT rate exceeds this 30% upper bound. This posterior probability of an RLT is calculated from the prior distribution, the number of subjects treated and the observed number of treatment-related RLTs.

Using these assumptions, the trial will be suspended if:

4 subjects experience treatment related RLT among the first 6 subjects enrolled or,

5 subjects experience treatment related RLT among the first 9 subjects enrolled or,

6 subjects experience treatment related RLT among the first 12 enrolled etc.

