5.2.2. Dose Modifications and Toxicity Management

The following toxicities, if they occur during Cycle 1 and are felt to be related to the protocol treatment, are considered to be dose-limiting toxicities (DLT) and are based on the Common Terminology Criteria for Adverse Events (CTCAE) version 5.0:

- a) Any death not clearly due to the underlying disease or extraneous causes
- b) Any AE leading to a dose delay of greater than 14 days in initiation of cycle 2 will be considered a DLT
- c) A DLT is specifically defined as any of the following toxicities that occur related to any of the study interventions (cisplatin, rintatolimod, pembrolizumab) or the combination (as assessed by the Investigator) that occurs during the first cycle of treatment:
 - 1. Grade 3 renal toxicity
 - 2. Grade 2 or greater bronchospasm
 - 3. Grade 2 or greater allergic reaction or generalized urticaria
 - 4. Grade 2 or greater autoimmune reaction
 - 5. Grade 3 injection site reactions
 - 6. Grade 3 anaphylaxis
 - 7. Grade 2 pneumonitis
 - 8. \geq Grade 3 hematologic toxicities lasting more than 48 hours, including neutropenia, thrombocytopenia and hemorrhage
 - 9. > Grade 3 non-hematologic toxicities
 - 10. Grade 3 neurological symptoms
 - 11. Fever > 41°C, uncontrolled for over 4 hours in the absence of a medical cause
 - 12. Grade 3 diarrhea, Grade 3 skin toxicity, or Grade 3 liver function test increase
 - 13. Evaluation of liver toxicity as defined by Hy's Law:
 - The drug causes hepatocellular injury, generally shown by a higher incidence of 3fold or greater elevations above the ULN of ALT or AST
 - Total Bilirubin>2xULN, without initial findings of cholestasis (elevated serum alkaline phosphatase)
 - No other reason can be found to explain the combination of increased ALT/AST and total bilirubin

31

A Dose Modification and toxicity management for immune-related AEs associated with pembrolizumab

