Nephritis: grading	Grade 2	Withhold	Administer corticosteroids (prednisone 1)	Monitor changes of renal function
according to increased creatinine or acute kidney injury	Grade 3 or 4	Permanently discontinue	to 2 mg/kg or equivalent) followed by taper	

irAEs	Toxicity Grade (CTCAE v5.0)	Action With Pembrolizumab	Corticosteroid and/or Other Therapies	Monitoring and Follow-up
Neurological Toxicities	Grade 2	Withhold	Based on severity of AE administer corticosteroids	Ensure adequate evaluation to confirm etiology and/or exclude other causes
	Grade 3 or 4	Permanently discontinue		
Myocarditis	Grade 1	Withhold	Based on severity of AE administer corticosteroids	Ensure adequate evaluation to confirm etiology and/or exclude other causes
	Grade 2, 3 or 4	Permanently discontinue		
Exfoliative Dermatologic Conditions	Suspected SJS, TEN, or DRESS	Withhold	Based on severity of AE administer corticosteroids	Ensure adequate evaluation to confirm etiology or exclude other causes
	Confirmed SJS, TEN, or DRESS	Permanently discontinue		
All Other irAEs	Persistent Grade 2	Withhold	Based on severity of AE administer corticosteroids	Ensure adequate evaluation to confirm etiology or exclude other causes
	Grade 3	Withhold or discontinue based on the event e		
	Recurrent Grade 3 or Grade 4	Permanently discontinue		

AE(s)=adverse event(s); ALT= alanine aminotransferase; AST=aspartate aminotransferase; CTCAE=Common Terminology Criteria for Adverse Events; DRESS=Drug Rash with Eosinophilia and Systemic Symptom; GI=gastrointestinal; IO=immuno-oncology; ir=immune related; IV=intravenous; SJS=Stevens-Johnson Syndrome; T1DM=type 1 diabetes mellitus; TEN=Toxic Epidermal Necrolysis; ULN=upper limit of normal.

$Note: Non-ir AE\ will\ be\ managed\ as\ appropriate,\ following\ clinical\ practice\ recommendations.$

- ^a AST/ALT: >3.0 to 5.0 x ULN if baseline normal; >3.0 to 5.0 x baseline, if baseline abnormal; bilirubin:>1.5 to 3.0 x ULN if baseline normal; >1.5 to 3.0 x baseline if baseline abnormal
- b AST/ALT: >5.0 to 20.0 x ULN, if baseline normal; >5.0 to 20.0 x baseline, if baseline abnormal; bilirubin: >3.0 to 10.0 x ULN if baseline normal; >3.0 to 10.0 x baseline if baseline abnormal

	Toxicity			
	Grade	Action With	Corticosteroid and/or Other	
irAEs	(CTCAE v5.0)	Pembrolizumab	Therapies	Monitoring and Follow-up

- ^c AST/ALT: >20.0 x ULN, if baseline normal; >20.0 x baseline, if baseline abnormal; bilirubin: >10.0 x ULN if baseline normal; >10.0 x baseline if baseline abnormal

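### DLT item 8 leaves a Grade 4 bleed controlled within 48 hours out of the suspension count, and item 13 cannot be decided for a single patient

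*Combined protocol and SAP*

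**What the plan says.** Section 8.1 suspends the trial, pending DSMC review, when the posterior probability that the RLT rate is 30% or more reaches .80. The prior is Beta(1.2, 2.8), and Table 8 lists the triggering counts. The rule refers to RLTs as already defined, but the only list above it is the DLT list, which Section 5.2.2 also carries.

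- **Item 8** (both lists) counts Grade 3 or higher "hematologic toxicities lasting more than 48 hours, including neutropenia, thrombocytopenia and hemorrhage".
- **Item 9** covers non-hematologic toxicity only. The threshold is Grade 3 or higher in Section 8.1 but above Grade 3 in Section 5.2.2.
- **Item 13** is headed as Hy's Law. Its first bullet in Section 8.1 is "The drug causes hepatocellular injury, generally shown by a higher incidence of 3-fold or greater elevations above the ULN of ALT or AST". The second requires bilirubin above 2x ULN without signs of cholestasis, identified by a raised alkaline phosphatase. Section 5.2.2 has a third bullet that Section 8.1 lacks: "No other reason can be found to explain the combination of increased ALT/AST and total bilirubin".
- **Section 7.2.3.2** defines a liver Event of Clinical Interest (ECI) for one patient: "an elevated AST or ALT lab value that is greater than or equal to 3X the upper limit of normal", bilirubin at least 2x ULN, and "an alkaline phosphatase lab value that is less than 2X the upper limit of normal".
- **Other routes to a DLT** are death (a), a delay of cycle 2 by more than 14 days (b), a Grade 2 or higher autoimmune reaction (item 4) and a Grade 3 liver test increase (item 12).
- **Outside the count**, Section 8.1 also allows suspension for toxicity that is both unexpected and serious, with no threshold given.

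**The concern.** Table 8 needs a yes or no for each treated patient, and the DLT list has to supply it. Item 8 puts hemorrhage among the hematologic toxicities and attaches a duration condition. That condition fits a laboratory cytopenia more naturally than a bleed, whose severity does not depend on lasting two days. Because item 9 is limited to non-hematologic events, it does not pick the bleed up. Under Section 8.1 a brief Grade 3 non-hematologic event counts, while a brief Grade 4 bleed does not. Section 7.2.4, Table 7 describes Grade 4 as "Life threatening consequences; urgent intervention indicated".

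The liver item has a different fault. Its first bullet describes how a drug behaves across many patients, so it gives no status to one patient in a single-arm trial. Its alkaline phosphatase condition also differs from the protocol's own patient-level flag for the same signal.

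At stake is the only quantitative safety stop for a three-drug combination. Section 7.1 itself notes the lack of information on that combination's safety and tolerability.

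**Working it through.** **1. The plan's own figures.** After r RLTs in n patients the posterior is Beta(1.2 + r, 2.8 + n − r). The trigger is the smallest r with P(π > .30) ≥ .80. All 14 boundaries in Table 8 reproduce, from 4/6 to 17/44. Of the 28 printed probabilities, 26 match. The exceptions are the posterior at 4/6 (printed .903, computed .922) and the binomial tail at 10/23 (printed .197, computed .120; .197 is the value for a 33% rate). Neither moves a boundary.

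**2. The bleed.** Take a related Grade 4 hemorrhage in cycle 1, stopped after 12 hours.

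- Item 8: not met, because it lasts less than 48 hours.
- Item 9: not met, because item 8 has named hemorrhage as hematologic.
- Item a: only if fatal.
- Item b: only if cycle 2 slips by more than 14 days.
- Otherwise it counts only if a consequence of the bleed meets another item, such as Grade 3 neurological symptoms.

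**3. The liver cases.** Values are multiples of ULN with a normal baseline. Table 3 footnote a gives Grade 2 as "AST/ALT: >3.0 to 5.0 x ULN if baseline normal" and bilirubin above 1.5 to 3.0x. Footnote b starts Grade 3 above 5x and above 3x respectively. Read literally, item 13 can be met by no single patient. The item 13 column below uses the charitable reading, as a patient-level test: ALT/AST at least 3x, bilirubin above 2x, alkaline phosphatase (ALP) not raised.

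| ALT / bilirubin / ALP | ECI (7.2.3.2) | Item 13, charitable | Grade 3 (items 9 in 8.1, 12) |
|---|---|---|---|
| 4 / 2.5 / 0.9 | yes | yes | no |
| 4 / 2.5 / 1.5 | yes | no (ALP raised) | no |
| 4 / 2.0 / 0.9 | yes | no (bilirubin not above 2x) | no |
| 6 / 2.5 / 1.5 | yes | no | yes |
| 4 / 3.5 / 1.5 | yes | no | yes |

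The second and third rows remain uncounted if the event is not judged autoimmune (item 4) and does not delay cycle 2 by more than 14 days (item b). The residue is ALT/AST of about 3 to 5x with bilirubin of about 2 to 3x.

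**4. Effect of one uncounted patient at a boundary.**

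| n | Trigger r | Posterior at r | Posterior at r − 1 |
|---|---|---|---|
| 6 | 4 | .922 | .773 |
| 9 | 5 | .904 | .762 |
| 12 | 6 | .890 | .757 |
| 17 | 8 | .903 | .799 |
| 20 | 9 | .896 | .796 |
| 29 | 12 | .883 | .794 |
| 44 | 17 | .873 | .798 |

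The other seven looks behave the same way: the value at r − 1 is below .80 at all 14.

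**5. Effect over the whole trial.** The documents give no rate for these events, so this is a range by assumption. Let p be the true rate and m the share of patients whose only qualifying event goes uncounted. The rule then sees p − m. An exact recursion over the 14 looks gives the probability of ever suspending.

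- p = 40%: .768 (m = 0), .729 (1 point), .687 (2), .643 (3), .550 (5).
- p = 35%: .550 (0), .454 (2), .317 (5).
- p = 50%: .975 (0), .956 (2), .910 (5).

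**The case against.** **Such events do not go unprotected.** A life-threatening bleed is a serious adverse event, reportable to the sponsor within 24 hours (Section 7.2.3.1). Section 8.1 allows suspension for unexpected and serious toxicity outside the count. Section 5.7 allows termination on the incidence or severity of adverse reactions, and Section 7.1 staggers the first three patients. This stands. A reader might infer that nothing else guards against these events, and the documents do not support that. However, these routes carry no numerical trigger and do not enter Table 8, so they do not correct the count.

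**The liver gap is thin.** This also stands. The uncounted cases are in the Grade 2 range, and an ECI may be non-serious. Section 7.2.3.2 presents its limits as a level that may call for further evaluation. Table 3 lists transaminase and bilirubin elevation as an immune-related event, and if it is so judged, item 4 counts it. Section 5.2.2 lets Grade 1–2 events continue only once resolved to Grade 1 or less by the next cycle, so persistent cases move toward item b. A reader might infer that every liver ECI ought to be a DLT, or that these cases are serious toxicity. No section says either.

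**Item 13 was meant for single patients.** The Hy's Law heading and the third bullet in Section 5.2.2 suggest so. That shows intent, but the first bullet still cannot be decided for one patient, and the third bullet is absent from the list in Section 8.1.

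**Any integer boundary flips on one event.** True. The boundary calculation shows that a misclassified patient can matter. It does not show how often one will occur.

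**Conclusion.** The bleed gap is firm on the wording of both lists: a related Grade 4 hemorrhage controlled within 48 hours enters the Table 8 count as no RLT, apart from the exceptions above. The liver gap is real but narrower: item 13 is undecidable as worded and conflicts with Section 7.2.3.2, leaving a small group of related, Grade 2-range, non-autoimmune cases with little delay that are ECIs but not DLTs.

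The tempting stronger reading is that the suspension rule undercounts serious toxicity to a material degree. The documents do not support it. They give no event frequency, several other items catch many of these cases, and the undercount is probably small. What can be said is that one uncounted patient at any boundary turns a suspension into a continuation. With an assumed true rate of 40% and 1 to 3 points uncounted, the chance of suspension falls from .77 to between .73 and .64.

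The conclusion also assumes that RLT means a DLT on this list, which Section 8.1 implies but never states.

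**What to change.** 1. Reconcile items 8 and 9 in Sections 5.2.2 and 8.1, including the differing grade threshold in item 9, so that every Grade 3 or higher hemorrhage has a definite and intended DLT status, including one shorter than 48 hours.
2. Reconcile item 13 in both lists, including the third bullet missing from Section 8.1, with Section 7.2.3.2, so that it can be decided from one patient's results. If the DLT and ECI definitions are meant to differ, say so and why.
3. State that RLT in Table 8 means a DLT on this list.

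The sponsor and its clinicians choose the clinical thresholds; none is proposed here. The cost is a few lines of wording in two sections, handled as a protocol amendment under Section 10.3.1, with no new data or visits. Patients already treated would need their DLT status checked against the reconciled list. The downside is that the RLT count, and so the chance of a suspension review, may rise slightly.
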